### 2 TRIAL OBJECTIVES

## 2.1 Primary Objective

To evaluate the objective response rate (ORR) to nivolumab in paediatric patients with refractory or recurrent hypermutated malignancies, including patients with replication repair deficiencies (RRD) such as constitutional mismatch repair deficiency (CMMRD).

## 2.2 Secondary Objectives

- 1. To determine the progression free survival (PFS) and overall survival (OS) of paediatric patients with progressive or recurrent hypermutated malignancies including RRD patients such as CMMRD, treated with nivolumab.
- 2. To evaluate safety and tolerability of nivolumab administered as a single agent at the adult recommended dose of 3 mg/kg every two (2) weeks. To define and describe the toxicities in paediatric patients with progressive or recurrent hypermutated malignancies including RRD patients, such as CMMRD.

# 2.3 Exploratory/Biology Objectives

- 1. To explore associations between TMB and response to nivolumab therapy.
- 2. To discover biomarkers predicting response of hypermutant cancers undergoing PD-1 blockade by investigating tumour neoantigen formation, specific T-cell receptor rearrangements (TCRR) of peripheral lymphocytes and tumour infiltrating lymphocytes (TILs), as well as a detailed characterization and activation of the immune infiltrations including the TILs.
- 3. To explore the use of minimally invasive methods to monitor and predict response to immune checkpoint inhibition in hypermutant cancers by investigating TCRR, phenotypic profiling of specific immune cells and their activation as a prognostic factor and variances throughout treatment as a response to therapy. As well, to investigate circulating tumour DNA (ctDNA) from serial peripheral blood samples as a surrogate marker of response.

### 3. STUDY DESIGN

## 3.1. Study Description

# **3.1.1** Study Overview

This is an open-label, single arm, multi-center, pilot study of nivolumab in paediatric patients with recurrent or refractory hypermutant malignancies aged 12 months to <25 years of age. Local centres are only obligated to treat/admit patients in accordance their age range capabilities.

The purpose of this study is to assess response of treatment with nivolumab in children with hypermutated cancers, including those with RRD, such as CMMRD syndrome.

This study will be performed in two parts: Part I – Molecular Profiling and Part II – Treatment and Companion Biomarker Studies.

In order to participate in **Part I**, patient's cancer specimen must undergo a specific gene sequencing panel to determine TMB or else have proof of RRD (as outlined below). Once TMB, or proof of RRD, is established and **Part II** eligibility is confirmed, patients will be stratified into cohorts based on levels of TMB or RRD status (for those patients for whom it is not possible to obtain TMB level) and patients will be enrolled to **Part II**.

#### Part I - Molecular Profiling

Patients with recurrent or relapse paediatric cancers that are suspected to be hypermutant (see **Part I** Inclusion Criteria in *Section 4.2.1* for exposition) will be consented to **Part I**, submit a specimen (as outlined in the *Lab Manual*) and undergo either the study-specific, next-generation sequencing (NGS) targeted gene panel to determine TMB level or only when sufficient neoplastic specimen is unavailable, provide proof of or tissue for diagnosis of an RRD disorder.

The TMB assay must be performed in a Study Chair or Co-chair specified, CLIA-certified laboratory. Proof of RRD status may be established by assays performed in either a CLIA or ISO 15189-certified laboratory in accordance with local regulations and at the discretion of the Study Chair or Co-chair. Proof of RRD includes functional mutation of polymerase genes (*POLE* and *POLD1*) or an MMR deficiency diagnosed by demonstrating a germline mutation or a loss of

MMR (MLH1, MSH2, MSH6, PMS2, EPCAM or MSH3) protein expression confirmed via negative immunohistochemistry (IHC) staining.

### Part II - Treatment and Companion Biomarker Studies

Patients with cancers that have been confirmed as hypermutant based on a report by a specific-TMB assay (acquired via **Part I** participation or previously) or have proof of RRD will be consented and enrolled into to **Part II**.

Cohort stratification of patients enrolled in **Part II** is based on their identified TMB levels or RRD status:

- Cohort A: TMB  $\geq$ 5 but <10 mutations/Mb (max. 20 patients);
- Cohort B: TMB  $\geq$ 10 mutations /Mb (max. 30 patients);
- Cohort C: unobtainable TMB in a patient with RRD.

N.B.: Patients stratified to Cohort C will be reallocated to Cohorts A or B if a TMB value subsequently becomes available.

All eligible patients will receive nivolumab intravenously (IV) at a dose of 3mg/kg administered every 14 days (two weeks). Two doses comprise one cycle (28 days or four weeks). Evaluations will be performed according to the schedule provided. Samples to perform 'Companion Biomarkers' research to further our understanding of paediatric hypermutant cancer response to nivolumab will be obtained (see *Lab Manual* for details).

N.B: We strongly recommend that all patients with confirmed or suspected RRD syndromes undergo screening for possible concurrent malignancies (see Section 8.0).

Patients will be monitored for toxicity using standard National Cancer Institute Common Terminology Criteria for Adverse Events (NCI CTCAE), version 4.03. Response assessment will use iRECIST criteria for solid tumours (modified for neuroblastoma using the revised INRC), iRANO criteria for CNS malignancies, RECIL 2017 criteria for lymphomas, revised criteria according to Creutzig, et al. (2012) for acute myeloid leukemia (AML; see *Section 10.13*), and criteria as specified in *Section 10.14* for acute lymphoblastic leukemia (ALL).

The Safety visit will be completed when the patient comes off treatment and prior to entering the Follow-Up Period.

## 3.2 Part II - Treatment and Companion Biomarker Study Duration

Nivolumab will be given in four (4) week cycles (one cycle equals two (2) drug administrations, two (2) weeks apart) for a maximum of up to two (2) years if clinical and radiological benefit is evident. After completion of treatment, patients will enter standard follow up for twelve (12) months. Patients with confirmed disease progression or excessive toxicity will discontinue treatment.

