# PROTOCOL SYNOPSIS

Protocol Title:	Pilot Study of Nivolumab in Pediatric Patients with Hypermutant				
Trotocor Title.	Cancers				
Protocol	SickKids Protocol No.: 1000053649				
Number:	Ozmosis Protocol No.: OZM-075				
Sponsor:	[name], The Hospital for Sick Children				
Phase of Development:	Pilot Study				
Methodology:	Single arm pilot study (proof of concept study)				
	Maximum duration of treatment: 24 months. Follow-up: 12 months.				
Study Duration:	Duration of enrollment: 24 months. Estimated duration of the whole				
	protocol: 60 months.				
	Primary Objective:				
	1. To evaluate the objective response rate (ORR) to nivolumab in				
	paediatric patients with refractory or recurrent hypermutated				
	malignancies, including patients with replication repair deficiencies				
	(RRD), such as constitutional mismatch repair deficiency				
	(CMMRD).				
Objectives:	Secondary Objectives:				
	1. To determine the progression free survival (PFS) and overall				
	survival (OS) of paediatric patients with progressive or recurrent				
	hypermutated malignancies, including RRD patients such as				
	CMMRD, treated with nivolumab.				
	2. To evaluate safety and tolerability of nivolumab administered as a				
	single agent at the adult recommended dose of 3 mg/kg every 2				
	weeks. To define and describe the toxicities in paediatric patients				

	with progressive or recurrent hypermutated malignancies including					
	RRD patients, such as CMMRD.					
	Companion Biomarker Exploratory Objectives:					
	1) To explore associations between tumour mutation burden (TMB)					
	and response to nivolumab.					
	2) To discover biomarkers predicting response of hypermutant					
	cancers undergoing PD-1 blockade by investigating tumour					
	neoantigen formation, specific T-cell receptor rearrangements					
	(TCRR) of tumour infiltrating lymphocytes (TILs) and detailed					
	characterization and activation of the immune infiltrations					
	including the TILs.					
	3) To explore the use of minimally invasive methods to monitor and					
	predict response to immune checkpoint inhibition in hypermutant					
	cancers by investigating TCRR, immuno-phenotypic profiling of					
	specific immune cells and their activation as a prognostic factor					
	and variances throughout treatment as a response to therapy. In					
	addition, investigating circulating tumour DNA (ctDNA) from					
	serial peripheral blood samples as a surrogate marker of response.					

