	response criteria for solid tumours (revised for neuroblastoma using the				
	revised INRC), iRANO response criteria for CNS malignancies, RECIL				
	2017 response criteria for lymphomas, revised criteria according to				
	Creutzig, et al. (2012) for acute myeloid leukemia (AML; see Section				
	10.13), and response criteria as specified in Section 10.14 for acute				
Criteria for	lymphoblastic leukemia (ALL).				
Efficacy	Patients with response of 'stable disease' (SD) will also be reported as part				
Evaluation:	of the final analysis of clinical benefit, but will not contribute to the				
	primary efficacy outcome measure.				
	Secondary efficacy outcome measures:				
	PFS is defined as the time from the first dose of the study drug				
	administration to the occurrence of disease progression or death from any cause during the study.				
	OS is defined as time from first dose of study drug to death from any				
	cause.				
	A safety evaluation by the Safety Committee will be performed after				
Criteria for	Patient 1-Cycle 1, Patient 4-Cycle 1, Patient 7-Cycle 1, and Patient 10-				
Safety	Cycle 1. Enrollment will be held after each time point until a safety				
Evaluation:	evaluation of adverse events (AE) and serious adverse events (SAE)				
	confirms it is safe to resume enrollment.				
	confirms it is safe to resume enrollment.				

Toxicities will be described and defined in paediatric patients, focusing on SAEs, using the National Cancer Institute Common Terminology Criteria for Adverse Events (NCI CTCAE), version 4.03. Toxicities (drug-related AEs) of any grade, plus all Grade  $\geq$  3 AEs, all Grade  $\geq$  3 laboratory toxicities and all SAEs as defined in *Section 12* will be collected for this study.

The initial aim for this pilot study was to accrue 20 paediatric patients with biallelic mismatch repair disease (bMMRD) tumours. Following amendment, the study inclusion criteria are expanded to include those with hypermutant tumours (as determined by estimation of TMB by targeted next-generation gene sequencing), as well as patients with CMMRD tumours. Consequently, the total enrollment will be increased to 50 patients.

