#### **8.4.1** Tumour Tissue

<sup>17These assessments for C1D1 pre-dose do not need to be repeated if these were done for baseline within seven (7) days prior to C1D1.

<sup>18 Assessments are to be done on days CXD1 ±2 days or CXD15 ±2 days on the day of and prior to nivolumab administration.

<sup>19 Samples may be taken up to 7 days prior to C1D1 dosing.

<sup>20 30 days after last dose.

<sup>21 Every 3 months for 1 year.

<sup>22 Unlike the *Companion Biomarkers*, if the CXD1 of cycle drug administration is delayed or omitted, all *Clinical Assessments* and *Laboratory/ Imaging Investigations* (and their respective windows) should adjust to the new CXD1, reflecting the patient's status prior to the upcoming drug administration. Please see respective footnotes above for details for changes to the *Companion Biomarker* assays.

In order to be included in **Part I** of the study, patients must have at minimum neoplastic specimen available as specified in the *Lab Manual*. With patient consent, said specimens will be assayed using NGS in a specific CLIA–certified laboratory approved by the Study Chair or Co-Chair to assess TMB for eligibility purposes. If this tissue is not available, but a TMB report from the specific CLIA–certified laboratory approved by the Study Chair or Co-Chair is already available, this information can be used for eligibility purposes. Whenever possible, both a fresh, formalin-fixed, paraffin-embedded tumour tissue sample and a fresh frozen tumour tissue sample are preferred to be used for TMB, other *Companion Biomarkers* studies and future biomedical research outlined above. Fresh frozen tissue is highly recommended for affiliated biomarker study once on trial. Please refer to *Lab Manual* for the detailed instructions for submission of the tissues.

In addition, all patients are also highly encouraged to submit paraffin embedded tumour sample to assess for MMR protein expression loss by IHC in a CLIA-certified environment for genes including, but not limited to MLH1, MSH2, MSH6, and PMS2. These results may also be used for inclusion to **Part II**, Cohort C (see above for details). As part of the *Companion Biomarker* studies in **Part II**, immune-related markers including but not limited to CD3, CD4, CD8, CD68, PD-1, and PD-L1 expression will also be assessed by IHC.

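### Follow-up ends 12 months after each patient stops treatment, so censoring for overall survival depends on outcome and the Kaplan-Meier curve is biased upward after about month 13

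*Protocol*

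**What the plan says.** The Synopsis, under secondary efficacy outcome measures, starts the survival clock at first dose: "OS is defined as time from first dose of study drug to death from any" cause. It sets no closing date.

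Follow-up uses a different origin. The Synopsis gives "Maximum duration of treatment: 24 months. Follow-up: 12 months", and Section 3.2 says "After completion of treatment, patients will enter standard follow up for twelve (12) months". Footnote 21 of the Part II study calendar (Section 8.2) sets the visits as "Every 3 months for 1 year", and footnote 12 gives disease assessments the same three-monthly spacing over one year.

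When follow-up starts depends on why treatment ends. Section 3.2 states: "Patients with confirmed disease progression or excessive toxicity will discontinue treatment". Section 3.1.1 sends everyone who stops into follow-up: "The Safety visit will be completed when the patient comes off treatment and prior to entering the Follow-Up Period".

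Nothing in the protocol extends survival follow-up to a common time from first dose. Section 12.3 asks for deaths later than 30 days after the last dose only when they are judged possibly drug-related. Section 13.1 asks sites to try to document outcome, in the setting of withdrawals and missed visits. Section 13.3 lists 30 days after the last dose, and entry to another anti-cancer trial, among the off-study criteria. That does not agree with a year of follow-up.

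**The concern.** Each patient's observation time is time on drug plus 12 months, and time on drug is itself a treatment outcome. Patients whose disease progresses early leave observation first, and they are the patients with the worse prognosis. Kaplan-Meier assumes that those censored alive have the same future risk as those still being followed. Here it would give the living early progressors the later survival of patients who stayed on nivolumab.

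The part of the curve affected is the tail beyond the first year. In a single-arm trial of a checkpoint inhibitor, in patients without known curative options, readers will give weight to late survival. Confidence intervals would not show the distortion, and no analysis plan can recover deaths that were never ascertained.

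**Working it through.** **Planned duration.** Enrolment 24 + treatment up to 24 + follow-up 12 = 60 months. This reproduces the Synopsis figure ("Duration of enrollment: 24 months. Estimated duration of the whole" "protocol: 60 months").

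**Observation per patient.** Last scheduled contact = months on treatment + 12. The first disease assessment is at the end of cycle 1, about month 1 (Section 8.2, footnote 12). Confirming progression takes a further 4 to 8 weeks in solid tumours (Section 10.4.2) and 3 months for early imaging progression in CNS tumours without substantial neurological decline (Section 10.9).
- Treatment stopped at month 1: 1 + 12 = month 13.
- Treatment stopped at month 4: 4 + 12 = month 16.
- Treated for 24 months: 24 + 12 = month 36.

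**Size of the bias.** The protocol gives no PFS, OS or post-progression survival for this population, so all survival inputs below are assumptions. Model 1: 35% of patients have long benefit (median PFS 36 months) and 65% have median PFS 2 months. OS = PFS + post-progression survival. All times are exponential. Censoring is at min(PFS, 24) + 12 months. Simulated Kaplan-Meier is compared with the true curve.

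With median post-progression survival of 9 months:
- 24 months: 50.2% against a true 40.7%, an overstatement of 50.2 − 40.7 = 9.5 points.
- 36 months: 43.9% against 27.9%, an overstatement of 43.9 − 27.9 = 16.0 points.
- 28% of patients are censored alive before month 24.

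Varying only post-progression survival, with no confirmation lag:

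| Median post-progression survival | Overstatement at 24 months | Overstatement at 36 months |
|---|---|---|
| 9 months | 9.5 points | 16.0 points |
| 4 months | 4.8 | 5.8 |
| 3 months | 2.8 | 3.1 |
| 2 months | 0.8 | 0.8 |

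Adding a 2- or 3-month lag before treatment stops, with a 9-month median, lowers the 24-month overstatement to about 6.5 or 5.4 points. With a 2-month median and the same lags it is below half a point at both times. OS at 12 months is unbiased throughout.

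**Model 2, as a cross-check.** Early progressors stop treatment at months 1 to 4 and responders are treated for 24 months. Responder share is 10 to 35%, median OS of progressors 6, 9 or 12 months, and of responders 36 or 60 months.
- The overstatement is 5.8 to 11.2 points at 24 months and 6.8 to 18.3 at 36 months. The largest values come from the 12-month progressor median.
- Control: with equal survival in both groups the bias disappears (25.0% estimated, 25.0% true at 24 months). The outcome-dependent censoring is therefore the cause.
- Censoring everyone at 36 months from first dose brings Kaplan-Meier to within about 0.3 points of the truth.
- If the 30-day criterion in Section 13.3 were applied instead, even 12-month OS would be overstated, by about 12 to 27 points.

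**The case against.** The strongest reply concerns size. Every survival rate above is assumed. Eligibility requires disease with no known curative therapy or therapy proven to prolong survival acceptably, so short post-progression survival is plausible and the bias may be near zero. Treatment also stops at confirmed rather than first progression, which lengthens observation. Both points stand, and they are why the range starts at about zero.

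Second, the protocol names neither Kaplan-Meier nor a 24- or 36-month OS estimate, and it does not say outright that deaths are unascertained after the follow-up year. This also stands in part: the finding applies to a standard OS curve drawn from the scheduled contacts. But no later contact is provided for, and the choice of estimator cannot supply missing vital status.

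Third, OS is secondary, with no hypothesis or decision rule, in a 50-patient pilot. Under the 9-month assumption the sampling standard deviation of 24-month OS is about 13 points with 20 patients and 10 with 30, as large as the bias or larger. That limits the importance. It does not cancel an error that runs in one direction.

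Two stronger readings are tempting. A reader might infer that the whole OS curve is unreliable from month 12, or that a late overstatement of about ten points is established. The protocol's assessment and confirmation times put the start of early progressors' censoring at about month 13 to 16, and its text contains nothing that fixes the size.

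**Conclusion.** The point holds in a limited form. Scheduled observation ends earlier for patients who stop early for progression or toxicity than for those with sustained benefit, so a standard Kaplan-Meier OS curve is biased upward after about month 13 whenever the early stoppers have the worse survival. Median OS is affected only if it falls beyond that time.

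Under assumed post-progression medians of 2 to 9 months, with 35% long benefit, the overstatement is about 0 to 10 points at 24 months and 0 to 16 at 36 months. It is larger with longer post-progression survival and smaller once a confirmation lag is allowed for. The direction was upward in every set tried in which prognosis differed.

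OS to month 12 is sound only if the 12-month follow-up is the rule actually applied, since Section 13.3 says otherwise. A reader might also infer that the trial's main conclusion is at risk. It is not: the cohort decisions rest on objective response, which this does not touch. This is an inexpensive improvement to a secondary endpoint.

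**What to change.** 1. In Sections 3.2 and 8.2, add vital-status contact by phone or chart about every 3 months for all treated patients until 36 months from first dose, whatever the treatment duration. Keep the existing post-treatment visits.
2. Reconcile Section 13.3 with Sections 3.2 and 8.2, so that neither the 30-day criterion nor entry to another anti-cancer study ends survival follow-up. Without this, the new contacts would conflict with the protocol.
3. Add matching consent wording, including for patients already enrolled where needed.
4. Where later vital status cannot be obtained, report OS estimates only to month 12, and only if the 12-month follow-up was in fact applied.

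The cost is modest site contact work and a consent update. Calendar time does not grow: a last patient entering at month 24 reaches 24 + 36 = month 60, the duration already planned.

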# 3.3 Independent Review Committee

Local ethics board/committee approval of the study must be obtained by a site/institution prior to enrolling and treating patients.

[figure not shown]
## 3.4 Data Safety Monitoring Board

A Data Safety Monitoring Board (DSMB) will be created following the study approval to evaluate the study for safety reasons.

The DSMB will review study data on a bi-annual basis and after the first 10 patients have been accrued. The DSMB may recommend that the trial stops after the inclusion of 10 patients based on toxicity and available efficacy data. A bi-annual careful review of treatment and patient safety will be undertaken by the DSMB and will include review of serious adverse events. The DSMB may recommend that the study stop earlier on the basis of safety concerns.

## 3.5 Study Flow Diagram

Children and Young Adults (CAYA); TMB = tumour mutation burden; RRD = replication repair deficiency; SickKids = The Hospital for Sick Children.

Figure 1. Study Design. The study is comprised of two parts: Part I – Molecular Profiling and Part II – Treatment and Companion Biomarker Studies.

- a. Recurrent or relapse paediatric cancer patients suspected to be hypermutant include those outlined in Section 4.2.1.
- b. A separate consent/ assent must be provided for **Parts I** and **II**. The **Part I Molecular Profiling** portion ensures that eligible patients meet the TMB threshold or RRD status necessary for stratification and progression to **Part II**.
- c. Cancer specimen (tumour, bone marrow or whole blood, as relevant) will be processed as outlined in the *Lab Manual*. All assays must be performed in a laboratory with specific certifications as outlined prior. If **Part I** consent is obtained prior to tumour acquisition, and sufficient tissue is available after all diagnostic and trial-related assays, efforts to process extra fresh tumour sample (prior to freezing/ fixation) immediately into viable cells should be made as outlined in the *Lab Manual*. If the patient is eligible, consents and is enrolled in **Part II**, these cells will be used as part of the "Companion Biomarker" research investigations. If the patient is not eligible or does not consent to **Part II**.
- d. A report from the specific, CLIA-certified laboratory (outlined in the *Lab Manual*) containing a TMB score may enter the screening process for **Part II** directly.
- e. If specimen is not available or a TMB result was not obtained in accordance with study guidelines, a patient with evidence of an RRD disorder will be eligible. Diagnosis of RRD includes proof of either a functional mutation of polymerase genes (*POLE* and *POLD1*) or an MMR deficiency diagnosed by demonstrating a germline mutation or a loss of MMR (MLH1, MSH2, MSH6, PMS2, EPCAM or MSH3) protein expression confirmed via negative immunohistochemistry (IHC) staining performed in an ISO 15189 or CLIA-certified laboratory depending on local regulation (see *Lab Manual*).
- f. As determined in specified, CLIA-approved laboratory (see Lab Manual).
- g. See Section 3.1.1 for Cohorts A & B details.
- h. A patient with proof of diagnosis of RRD may be recruited to Cohort C as outlined in *Section 3.1.1* and the *Lab Manual*. If tumour tissue becomes available while on study, a TMB assay will be performed and these patients may be reallocated to Cohorts A or B. Patients will only remain in Cohort C if impossible to obtain a TMB in perpetuity.
- A separate consent/ assent must be provided for Parts I and II. During the Part II Treatment and Companion Biomarker Studies portion, patients enrolled will receive nivolumab (as specified above) and provide samples for accompanying biomarker research (see Section 2.3, 8.2 and the Lab Manual).

